### **5.3.5 Secondary Endpoint 5**

Secondary endpoint 5 examines the overall incidence of serious adverse events that meet primary endpoint 1 criteria as separated by each Corox LV lead model. The overall incidence of the serious adverse events meeting primary endpoint 1 criteria will be reported for each lead model using the subject population defined in section 3.3 Secondary Endpoint Per-Protocol (PP) Analysis Populations.

Similar to primary endpoint 1, secondary endpoint 5 will also be evaluated by performing an exact, noninferiority test comparing a binomial proportion (overall serious adverse event free-rate at 5 years) to 92.5%, with a noninferiority delta of 5% (87.5%). A p-value will also be reported.

Additionally a Kaplan-Meier actuarial graph and case summary will be reported for each lead model. Furthermore, the estimated freedom from adverse event at 5 years along with the standard error and 95% confidence intervals will also be reported for each lead model.

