2.7.2 Missing Data

The reasons for any missing data in the study will be documented. The sponsor will examine both missing-data patterns, which describe which values are observed and which are missing, and the missing-data mechanisms, which concern the relationship between missingness and the values of variables in the study data set [R.J.A. Little and D.B. Rubin, 2002, Statistical Analysis with Missing Data, 2nd edition, Wiley and Sons].

For evaluation of the primary study endpoints (safety endpoints 1 and 2), only patients who achieve 5 years of follow-up or have experienced a serious adverse event prior to 5 years will be included in the evaluation of the associated hypotheses. The secondary endpoint of other SAEs at 5 years, excluded from the primary safety analyses, will be analyzed in similar manner. There will be no imputation for these missing adverse event outcomes.

For purposes of Kaplan-Meier actuarial analyses, described in Section 2.7.1 Trend Analyses, all SAE data on enrolled patients will be included, with follow-up time censored at the time of withdrawal or last completed follow-up visit.

Secondary endpoints, which include successful biventricular pacing, pacing thresholds, sensing and impedance measurements will be analyzed in two ways. Initially, all available results will be summarized by scheduled visit through the 5 years of study follow-up. Afterwards, a last value carried forward (LVCF) will be used to estimate the values at the final 5-year follow-up evaluation.

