### 3. ANALYSIS POPULATIONS

The primary and secondary endpoints analyses will be conducted based on pre-defined populations as described below.

The primary endpoint per-protocol analysis population will be used to conduct the primary endpoints 1 and 2 analyses because these endpoints are based on SAEFR and SAE rates at 5 years post-implant respectively. The secondary endpoint per-protocol analysis population will be used to conduct the secondary endpoints 5 and 6 analyses because these endpoints examine primary endpoints 1 and 2 based on originally implanted lead models; therefore, are examined at 5 years post-implant. The intention-to-treat population will be used to conduct the secondary endpoints 1 through 4 analyses and all additional data of interest because these endpoints are continuous and examine measurements and event rates throughout the study; therefore, are not limited to only examining subjects who complete 5 year follow-up.

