#### 3.2 PRIMARY ENDPOINT PER-PROTOCOL (PP) ANALYSIS POPULATION

The primary endpoint per-protocol (PP) population is a subset of the ITT population. The primary endpoint PP subjects have experienced a protocol defined primary endpoint AE or have a follow-up visit or system revision date completed 5 years post-implant (defined as a visit completed on or after 45 days prior to the 5 year post-implant date, 1781 days).

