#### 3.3 SECONDARY ENDPOINT PER-PROTOCOL (PP) ANALYSIS POPULATIONS

The secondary endpoint per-protocol subjects are a subset of the primary endpoint PP population, who are separated by the originally implanted Corox LV lead models. Subjects with a Corox LV lead replacement resulting in a change in lead model (e.g. Corox OTW-S BP to Corox OTW-L BP) and experiencing an event after the replacement will be analyzed with the originally implanted lead.

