##### 3.3.2 Corox OTW-S BP (Screw) PP Analysis Population

The Corox OTW BP-S (screw) PP subjects are originally implanted with a Corox OTW BP-S (screw) lead and have experienced a protocol defined AE or have a follow-up visit or system revision date completed 5 years post-implant (defined as a visit completed on or after 45 days prior to the 5 year post-implant date, 1781 days).

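### As written, the by-model Kaplan-Meier estimates for secondary endpoint 5 fall on the per-protocol set, which omits SAE-free early leavers and so overstates each model's 5-year SAE rate

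*SAP*

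**What the plan says.** SAP section 3 allocates populations by endpoint: "The secondary endpoint per-protocol analysis population will be used to conduct the secondary endpoints 5 and 6 analyses". SAP 5.3.5 applies this to the by-model incidence, which "will be reported for each lead model using the subject population defined in section 3.3 Secondary Endpoint Per-Protocol (PP) Analysis Populations". After describing the exact test, it continues: "Additionally a Kaplan-Meier actuarial graph and case summary will be reported for each lead model". It then adds: "the estimated freedom from adverse event at 5 years along with the standard error and 95% confidence intervals will also be reported for each lead". Neither of the last two sentences names a population.

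Entry to the primary per-protocol set is defined in SAP 3.2. Its subjects "have experienced a protocol defined primary endpoint AE or have a follow-up visit or system revision date completed 5 years post-implant", where the visit must fall on day 1781 or later. SAP 3.3 states that "The secondary endpoint per-protocol subjects are a subset of the primary endpoint PP population", split by the originally implanted model. SAP 3.3.1 and 3.3.3 repeat the 3.2 rule. SAP 3.3.2, for OTW-S, is looser: its subjects "have experienced a protocol defined AE or have a follow-up visit or system revision date completed 5 years post-implant", without the restriction to primary-endpoint events.

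The SAP's other Kaplan-Meier estimates, in 5.3.2 (secondary endpoint 2) and 5.4 (the FDA-requested analysis), are explicitly on the ITT population. For the Kaplan-Meier trend analyses, Protocol 2.7.2 says "all SAE data on enrolled patients will be included, with follow-up time censored at the time of withdrawal or last completed follow-up visit".

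**The concern.** Kaplan-Meier uses subjects who leave early without an event by counting them as at risk until they leave. The per-protocol set removes those subjects and keeps anyone who had an event before leaving, so membership depends on the outcome. Run on that set, the curve has almost nothing left to censor before 5 years.

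Two things are at stake. First, 5.3.5 would show a crude proportion and a Kaplan-Meier estimate that look like two analyses but are nearly one. The second would appear to account for attrition when it does not. Second, the endpoint exists to describe the three lead models separately. Because the bias varies with each model's attrition and SAE timing, models with the same true rate could show different figures. Nor would those figures be comparable with the SAP's ITT-based estimates or with the protocol's pooled trend curves.

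**Working it through.** **Inputs.** The 5-year SAE-free rate of 92.5% (SAE rate p = 7.5%) and the 50% loss over 5 years come from SAP 1.1 and 5.6. Protocol 2.6 calls the 50% a maximum and counts all exits in it, including death and explant. The documents give no SAE timing, no observed attrition, no attrition by model, and no figure for the bias examined here.

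**The plan's own figure.** These inputs come from the endpoint 1 sample size, which reproduces. With 240 subjects, a null rate of 87.5% and an alternative of 92.5%, the exact binomial rule (at least 219 SAE-free) has one-sided alpha 0.0436 and power 80.7%. Then 240/0.5 = 480 enrolled.

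**Formula.** Let f(t) be the SAE density and G(t) the proportion still in follow-up, with loss independent of SAE risk. As shares of those enrolled:

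- E = integral of f(t)G(t) from 0 to 5 years (SAE seen before exit)
- F = (1 − p)G(5) (SAE-free completers)
- Expected 5-year SAE estimate in the per-protocol set = E/(E + F)

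Since G(t) ≥ G(5), E is at least pG(5), so E/(E + F) is at least p. The bias is never downward under independent loss.

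**Constant hazards.** Let λ = −ln(0.925)/5 = 0.01559 and μ = −ln(G(5))/5. Then E = λ/(λ + μ) × [1 − 0.925·G(5)]. At 50% loss, μ = 0.13863, so E = 0.1011 × 0.5375 = 0.0543 and F = 0.925 × 0.5 = 0.4625.

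| Loss by 5 years | E | F | E/(E + F) | Against 7.5% |
|---|---|---|---|---|
| 50% | 0.0543 | 0.4625 | 10.5% | +40% |
| 41% (10% a year compounded: 1 − 0.9⁵) | 0.0585 | 0.5462 | 9.7% | +29% |
| 30% | 0.0632 | 0.6475 | 8.9% | +19% |
| 20% | 0.0673 | 0.7400 | 8.3% | +11% |

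If the 50% loss is linear (10% of those enrolled each year), the first row becomes 10.9% (+45%).

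**SAE timing at 50% loss, true rate 7.5%** (ranges run from exponential to linear loss):

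| SAE timing | Bias |
|---|---|
| All at the start: 0.075/(0.075 + 0.4625) = 13.95% | +86% |
| All in year 1 | +75% to +78% |
| Falling hazard (Weibull shape 0.5) | +55% to +59% |
| Constant hazard | +40% to +45% |
| Rising hazard (Weibull shape 2) | +26% to +31% |
| All in year 5 | +7% to +9% |
| All at 5 years: 0.0375/(0.0375 + 0.4625) = 7.5% | 0% |

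**Check with the day-1781 rule.** A simulation of 400,000 subjects with constant SAE hazard and exponential loss to 50% gave 7.6% for Kaplan-Meier on all enrolled and 10.4% for Kaplan-Meier on the per-protocol set (1.38 times). The crude per-protocol proportion was also 10.4%. Linear loss gave 7.5%, 10.7% (1.42 times) and 10.7%. So the per-protocol curve does reduce to the crude proportion, while the all-enrolled curve recovers the true rate.

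**Comparison between models.** Two models with the same true rate of 7.5% and constant hazards, one losing 30% and the other 50%, would show 8.9% and 10.5%. The gap would come from attrition alone.

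**The case against.** The strongest reply is that the Kaplan-Meier sentences in 5.3.5 name no population, since the per-protocol reference belongs to the incidence sentence. That is true. But section 3 assigns the endpoint 5 analyses as a whole, and 5.3.2 and 5.4 state ITT where ITT is meant. A programmer following the SAP would use the per-protocol set. If ITT was intended, the text still needs correcting.

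A reader might infer that the protocol requires ITT here. It does not say so. The rule in Protocol 2.7.2, repeated in 7.6, is scoped to the trend analyses of 2.7.1, and the by-model curve is an SAP addition. The conflict is one of consistency.

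A reader might also infer that the by-model comparison with 87.5% is damaged by this point and repaired by the fix. It is not. That is an exact binomial test. Protocol 2.7.2 restricts the primary hypotheses to completers or subjects with an SAE, and Protocol 2.7 applies the primary criteria to each model. The Kaplan-Meier population leaves that test unchanged.

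It also stands that the consequence is limited. SAP 2.3 and 5.3 attach no formal hypothesis to the secondary endpoints, the bias works against the device, and pooled all-enrolled curves are still produced at the reporting intervals. Nor is the all-enrolled curve free of assumptions. It needs loss to be independent of SAE risk, and because death counts as loss, it estimates the rate as if death did not compete.

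**Conclusion.** The point holds for the by-model Kaplan-Meier graph, 5-year freedom estimate, standard error and confidence interval. Followed as written, the SAP would overstate each model's 5-year SAE rate. The direction rests only on loss being independent of SAE risk.

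The size is not fixed by the documents. The +40% is an illustration at a true rate of 7.5%, constant hazards and the full 50% loss. A reader might take it as a flat correction for every model, but attrition and SAE timing by model are unknown, and timing alone spans about 0% to +86% at 50% loss. The calculation also ignores delayed entry (enrollment 7 to 180 days after implant).

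Nor are all SAE-free early leavers certain to be excluded for OTW-S. The wording of 3.3.2 could admit one who had some other protocol-defined event, which contradicts the subset statement in 3.3.

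This affects by-model safety reporting. It changes no primary conclusion.

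**What to change.** In SAP sections 3 and 5.3.5, state that the by-model Kaplan-Meier graph, 5-year freedom estimate, standard error and confidence interval use all enrolled (ITT) subjects, grouped by originally implanted model and censored at withdrawal or last completed follow-up visit. This matches SAP 5.3.2 and 5.4 and the protocol's trend-analysis rule. Leave the exact binomial test on the per-protocol set.

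In SAP 3.3.2, restrict the event criterion to primary-endpoint events so that it agrees with 3.2, 3.3, 3.3.1 and 3.3.3.

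The cost is a sentence in each of sections 3 and 5.3.5 and a short wording correction in 3.3.2. No new data are needed.

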### **5.3.6 Secondary Endpoint 6**

Secondary endpoint 6 examines the individual incidence of serious adverse events that meet primary endpoint 1 criteria as separated by each Corox LV lead model. The individual incidence of the serious adverse events meeting primary endpoint 1 criteria will be reported for each lead model using the subject population defined in section 3.3 Secondary Endpoint Per-Protocol (PP) Analysis Populations.

Similar to primary endpoint 2, secondary endpoint 6 will also be evaluated based on the exact, two-sided 95% confidence interval for the observed, individual serious adverse event rates at 5 years. The upper bound of these 95% confidence intervals will be compared to 1%.

## **5.4 FDA REQUESTED AD HOC ANALYSIS**

The FDA requested ad hoc analysis examines the overall incidence of events defined in section 2.4. The FDA defined event rates will be reported along with a Kaplan-Meier actuarial graph and case summary will be reported to assess this analysis. The estimated freedom from adverse event at 5 years along with the standard error and 95% confidence intervals will also be reported. This endpoint will be evaluated using the subject population defined in section 3.1 Intention-to-Treat (ITT) Analysis Population.

## **5.5 FIGURES, TABLES, AND LISTINGS TEMPLATES**

Refer to the CELESTIAL Final Clinical Report Template

## **5.6 ADHERENCE AND RETENTION ANALYSIS**

A 50% loss to follow-up over 5 years (10% per year) will be assumed.

## **5.7 ADDITIONAL SUB-GROUP ANALYSES (IF APPLICABLE)**

No additional sub-group analyses are pre-specified. If any additional sub-group analyses are done, descriptive statistics only will be reported with no hypotheses tests.

